In accordance with ICH/GCP reporting guidelines and ISO/DIS 14155 draft standard, Adverse Events (AEs), Serious Adverse Events (SAEs), Adverse Device Effect (ADEs), Serious Adverse Device Effect (SADEs), and Unanticipated Serious Adverse Device Effect (USADEs) will be collected and recorded throughout the duration of the trial. The investigator and facility should report all AEs, SAEs, which are not device attributed in line with facilities internal adverse event reporting procedures.

The investigator *should not* report device attributed events without prior consultation with the study's Medical Monitor. The investigator is also responsible for ensuring that all AEs and SAEs are recorded on the Adverse Event Log and all reportable ADEs (ADEs, SADEs, USADEs) are recorded and reported to the Sponsor in accordance with instructions in this section.

Device attributed adverse events, device attributed serious adverse events and device attributed unexpected adverse events will be reported by the Sponsor of the clinical trial in line with current FDA regulatory requirements.

Definitions for safety reporting purposes in this trial are as follows:

[figure not shown]
- **Adverse Event:** Any untoward medical occurrence in a subject or clinical investigation which does not necessarily have a causal relationship with the medical device under investigation.
- Serious Adverse Event: An adverse event that results in one of the following outcomes: requires
 hospitalization; prolongs hospitalization; is life-threatening; results in congenital anomaly/birth defect;
 results in death.

Study Number IRR-CT-901-2013-01	Version: 1.0	01AUG2014
© Confidential IrriMax Corporation		Page 22 of 35

- Adverse Device Effect: An adverse event that results from the presence or performance of the device or any component of the system.
- **Serious Adverse Device Effect:** An adverse event related to the presence or performance of the device or any component of the system that results in one of the following outcomes: requires hospitalization; prolongs hospitalization; is life-threatening; results in congenital anomaly/birth defect; results in death.

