- Recorded data from automated instruments such as (ECGs, rhythm strips, electroencephalograms (EEGs), pulmonary function tests, etc.)
- Records of telephone contacts
- Evaluations checklists
- Study Product distribution and accountability logs maintained by study personnel
- Correspondence between physicians or memoranda to IRBs/IECs regarding any subject's treatment

Statistical Methodology:

Endpoints

Efficacy

Primary

The primary efficacy endpoint is the rate of SSI observed within 30 days from the date of index operation.

Secondary

The secondary efficacy endpoints will include the following:

- The length of stay in the hospital
- Rate of readmission to the hospital, within 30 days from the date of the index operation
- Estimated costs of the index hospitalization

Exploratory Endpoints

The following outcomes will be reviewed as exploratory endpoints:

- Superficial surgical site infection (SSI)
- Deep surgical site infection (SSI)
- Organ/space surgical site infection (SSI)
- Ventilator associated pneumonia (VAP)
- Catheter associated urinary tract infection (CAUTI)
- Central line associated blood stream infection (CLABSI)
- Deep vein thrombosis (DVT)
- Pulmonary embolus (PE)
- Acute cardiac event

Study Number IRR-CT-901-2013-01	Version: 1.0	01AUG2014
© Confidential IrriMax Corporation		Page 27 of 35

- Clostridium difficile (C-diff) infection
- MRSA infection
- Mortality

Safety

The safety of the IrriSept irrigation unit will be assessed through the clinical review and analysis of adverse events.

Randomization

Subjects who meet all inclusion and exclusion criteria will be centrally randomized in the OR in a 1:1 ratio to either the study product group or the control group, in accordance with a computer-generated block randomization schedule prepared by a non-study statistician. A unique randomization number and associated treatment assignment will be made using an interactive web-based response system (IWRS). Randomization will be stratified by center with no center allowed to enroll more than 120 subjects.

Statistical Methods

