This section outlines the statistical analysis strategy and procedures for the study. If, after the study has begun, changes are made to primary and/or key secondary hypotheses, or the statistical methods related to those hypotheses, then the protocol will be amended (consistent with ICH Guideline E-9). Changes to exploratory or other non-confirmatory analyses made after the protocol has been finalized, along with an explanation as to when and why they occurred, will be listed in the Clinical Study Report (CSR) for the study. Post hoc exploratory analyses will be clearly identified in the CSR. A separate Statistical Analysis Plan (SAP) with further details than presented here will be finalized prior to first patient enrolled to minimize any bias, as the study is non-blinded.

Power and Sample Size

The determination of sample size for this study is based on the primary objective to demonstrate the superiority of the IrriSept irrigation unit versus conventional standard of care in patients who undergo open abdominal laparotomy for abdominal trauma or acute surgical abdomen within 36 hours of initial presentation to their healthcare organization. The primary endpoint is the rate of SSI observed within 30 days (+/- 3 days) from the date of the index operation.

Based on historical data, it is assumed that the rate of SSI within the standard of care group will be \geq 20%. A total of 600 patients (300 per group) will provide \geq 90% power to demonstrate a reduction in the rate of SSI, up to 50%, assuming a control group rate for SSI of \geq 20%, based on a two-sided Chi-square test with a 5% significance level. The following table shows the power achieved under various combinations of control group SSI rates and relative treatment differences.

Table 2.1: Power associated with a total sample size of 600 (n=300/group), based on a two-sided Chi-square test with a 5% significance level.

Control Group SSI	Relative Treatment Difference (IrriSept/Control)		
Rate	50% Reduction	40% Reduction	30% Reduction
15%	83%	62%	38%
20%	93%	76%	50%
25%	98%	87%	61%

It is anticipated that approximately 1100 patients will be screened, 650 patients will be enrolled, to obtain 600 evaluable patients, based on a non-evaluable rate of approximately 5%. All calculations were carried out in SAS version 9.2 using the comparison for two independent proportions procedure in PROC POWER.

Study Number IRR-CT-901-2013-01	Version: 1.0	01AUG2014

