Univariate assessment of categorical risk factors and of continuous risk factors will be assessed to identify whether differences exist between the two populations of patients in the frequency of independent variables following patient randomization. Risk factors with P<0.05 on univariate analysis will then be used to create a forward stepwise logistic regression model to predict SSI. Hospital dummy variables will be employed to remove hospital effects. Logistic coefficients will be defined for the clinical variables including the use of the IrriSept irrigation system. Odds ratios and confidence intervals will be established to evaluate statistical significance, or lack thereof, of the IrriSept system. An additional benefit of this modeling will be the development of risk equations that combine administrative, clinical, and laboratory data into the prediction of SSI in this population of patients.

Multiplicity

As there is a single primary endpoint, and no formal unblinded interim analyses that will utilize the primary endpoint to modify the trial, no adjustment for multiplicity is planned. No adjustment for multiplicity is planned for the analysis of secondary endpoints

Sub-groups

To determine whether the treatment effect is consistent across various subgroups, the estimate of the odds ratio (and 95% CI) for the primary endpoint will be estimated and displayed using forest plots for the following sub-groups:

- Age category (≤65 vs. >65 years)
- Gender (female, male)
- Emergency laparotomy for trauma exclusively vs. laparotomy for emergency general surgery

For the analysis of each sub-group, a logistic regression model for the primary endpoint will be used, with terms for treatment group, the sub-group and the sub-group by treatment interaction. The odds ratios and 95% CI's within each sub-group category will be reported, along with the p-value for the interaction term.

Safety Analyses

All safety analyses will be presented using the safety analysis set. No formal hypothesis testing will be conducted.

Adverse Events

Adverse events will be coded using MedDRA (Version 17.x). All AEs that occur after the start of surgery (cut time) will be summarized using frequency counts and percentages. Summaries will be presented by treatment

Study Number IRR-CT-901-2013-01	Version: 1.0	01AUG2014
© Confidential IrriMax Corporation		Page 30 of 35

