group using the MedDRA level hierarchy (system organ class, high level group term, high level term, and preferred term) as follows:

- Overall (i.e., regardless of severity or relationship to treatment)
- By severity grade (mild, moderate, severe, or life threatening)
- By relationship to study product (potential relationship to study product or unlikely/no relationship to study product) according to the mapping scheme below:
 - o Potentially related: will include all AEs with a relationship rating of "definite", "probably" or "possibly."
 - Unlikely/not related: will include all AEs with a relationship rating of "unlikely" or "unrelated."

Unless otherwise specified, at each level of patient summarization in reporting the incidence of the AEs, a subject will be counted once if the subject reported one or more events. If more than one occurrence of an event is reported, the event of the worst severity or the worst-case relationship assessment will be summarized.

AEs leading to premature discontinuation and serious AEs (SAEs) will also be summarized by treatment group and relationship. AEs leading to premature discontinuation will be defined as any AE with an action taken equal to "permanently discontinued."

Demographics and Baseline Summaries

Demographic variables (e.g., age, gender, race, ethnicity) and baseline characteristics (e.g., medical history, PATI, AIS and ASA scores, adherence to SCIP prophylactic antibiotic-specific guidelines, surgical skin preparation used, shock, (systolic BP < 90 mm Hg), intubation, active infection, transfusion of blood/blood products, primary injury in trauma or primary organ(s) in the acute abdomen and intraoperative risk factors), will be summarized by treatment group. The comparability of the treatment groups for relevant demographic and baseline characteristics will be assessed by descriptive statistics. No statistical hypothesis tests will be performed. For continuous data, summaries will include the number of observations, mean, standard deviation, median, 25th and 75th quartiles, minimum and maximum values. For categorical data, frequency counts and percentages will be reported.

Concomitant Medications/Antibiotics

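### Pooled AE and SAE incidences by arm do not exclude SSI, so a fall in SSI can offset a rise in other adverse events in those rows, most importantly for SAEs

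*Combined protocol and SAP*

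**What the plan says.** All references are to the protocol, which contains the statistical section.

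- **Definition.** An adverse event is "Any untoward medical occurrence in a subject or clinical investigation", whether or not the device caused it. It becomes serious if it requires or prolongs hospitalization, is life-threatening, or results in a birth defect or death. SSI is not carved out of either definition.
- **Recording.** Adverse Event Documentation requires every AE to go into the source document and onto the AE log. Visit 2 lists documentation of SSI and documentation of AEs as separate items.
- **Tabulation.** Under Safety Analyses, Adverse Events: "All AEs that occur after the start of surgery (cut time) will be summarized using frequency counts and percentages". The summaries follow the MedDRA hierarchy by treatment group. They are given "Overall (i.e., regardless of severity or relationship to treatment", by severity and by relationship to product, and a subject counts once at each level. SAEs are summarized by treatment group and relationship; no term-level SAE breakdown is stated. No formal safety testing is planned.
- **Role of AEs.** Under Endpoints, Safety: "The safety of the IrriSept irrigation unit will be assessed through the clinical review and analysis of adverse events".
- **Planned effect on SSI.** Under Power and Sample Size, "it is assumed that the rate of SSI within the standard of care group will be" at least 20%, and the trial is sized to "demonstrate a reduction in the rate of SSI, up to 50%, assuming a control group rate for SSI of" at least 20%.

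**The concern.** SSI is both the event the device is meant to prevent and, on the protocol's wording, an adverse event. Section 1.2 says an SSI adds 7 to 10 days of stay on average, so an appreciable share may also meet the prolonged-hospitalization criterion for an SAE.

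Any pooled incidence that counts a subject once for one or more events then mixes two quantities: the benefit on SSI and any harm of another kind. If the benefit is real, the IrriSept arm starts with a lower pooled rate, and an excess of other events can leave that rate level. Term-level lines cannot be added up to recover the number of subjects with any non-SSI event, because subjects overlap between terms. The missing figure is therefore not available from the planned tables, although the data behind it are collected.

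**Working it through.** **Inputs from the protocol.** Control SSI 20% and a 50% relative reduction, giving 10% on IrriSept. "A total of 600 patients (300 per group) will provide" at least 90% power, "based on a two-sided Chi-square test with a 5% significance level".

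**Reproducing the plan's figure.** With the pooled-variance normal approximation, n = 300 per arm, 20% v 10%:

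z = [0.10·√300 − 1.96·√(2·0.15·0.85)] / √(0.20·0.80 + 0.10·0.90) = (1.732 − 0.990)/0.500 = 1.48

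Power is 93.1%, against 93% in Table 2.1. The other eight cells also agree to within one point.

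**Assumptions not in the protocol.** The non-SSI AE incidence q in control; independence of SSI and other AEs; the share s of SSIs that are serious. Each of q and s is shown as a range.

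**Any AE.** Let q′ be the non-SSI AE incidence on IrriSept.

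- Control: 1 − 0.80(1 − q)
- IrriSept: 1 − 0.90(1 − q′)
- Equal when q′ = 1 − (0.80/0.90)(1 − q), so the hidden rise is q′ − q = (1 − q)/9

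| q (assumed) | q′ at equality | Hidden rise, points | Any-AE incidence, both arms |
|---|---|---|---|
| 10% | 20.0% | 10.0 | 28% |
| 20% | 28.9% | 8.9 | 36% |
| 30% | 37.8% | 7.8 | 44% |
| 50% | 55.6% | 5.6 | 60% |
| 70% | 73.3% | 3.3 | 76% |

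Per 300 subjects, the first row is 30 more with a non-SSI AE and the last row is 10 more.

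**Smaller SSI effect, q = 30%.**

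- 40% reduction (20% v 12%): q′ = 1 − (0.80/0.88)(0.70) = 36.4%, hiding 6.4 points.
- 30% reduction (20% v 14%): q′ = 1 − (0.80/0.86)(0.70) = 34.9%, hiding 4.9 points.

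**Overlap.** If SSI and other AEs never occurred in the same subject, equality requires q + 20 = q′ + 10, and the full 10 points are hidden at any q. If every subject with an SSI also had another AE, nothing is hidden.

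**SAEs, non-SSI SAE rate 10% (assumed).** Only serious SSIs count, so q′ = 1 − [(1 − 0.20s)/(1 − 0.10s)](0.90).

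| s (assumed) | Serious SSI, control v IrriSept | q′ at equality | Hidden rise, points |
|---|---|---|---|
| 25% | 5% v 2.5% | 12.3% | 2.3 |
| 50% | 10% v 5% | 14.7% | 4.7 |
| 75% | 15% v 7.5% | 17.3% | 7.3 |
| 100% | 20% v 10% | 20.0% | 10.0 |

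**What excluding SSI would show.** The same rises would appear at full size. If they were tested at a two-sided 5% level with 300 per arm, nominal power would be 93% at q = 10% and 15% at q = 70%. The extra rows make the excess visible, but do not make a small one conclusive.

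**The case against.** The strongest case against has five parts.

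1. **Inclusion of SSI is inferred.** Visit 2 and the schedule of events list SSI and AE documentation separately. Reporting detail is deferred to the study reference binder, CRF guidelines and a separate SAP. This stands as a caveat. It does not remove the point: nothing in the text says an SSI is not also an AE, and if sites differ in logging them the pooled rows become harder still to read.
2. **No headline comparison is designated.** A reader might infer that the safety conclusion turns on one any-AE row. The protocol does not say so. Its overall summary is a version of the MedDRA table, and other classes and preferred terms are unaffected by SSI. This stands.
3. **Other views of harm exist.** A reader might infer that non-SSI harm would be invisible. It would not be. Pneumonia, catheter and line infections, thrombosis, embolism, cardiac events, *C. difficile* and mortality are separate exploratory endpoints. Device effects are captured separately, and safety includes clinical review. This stands, and confines the problem to pooled rows. Relationship splits help less, because causality is judged by investigators in an open-label trial whose control subjects receive no study product.
4. **The sizes are break-even values.** They need the planned SSI effect and assumed background rates. At q = 90% the hidden rise is only (1 − 0.90)/9 = 1.1 points. This stands; hence the ranges.
5. **A non-SSI set is imperfect.** Serious sequelae of an SSI are recorded as events of their own and would remain in it. Resting the safety conclusion on that set alone would also discount SSI if the device worsened it. Both stand, and both shape the fix.

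**Conclusion.** The point holds for the pooled subject-level AE and SAE incidences by arm. As written, SSIs logged as AEs enter those rows. At the planned SSI effect, the any-AE incidence can be level while other AEs rise by about 3 to 10 points (non-SSI AE rates of 70% down to 10%, independence assumed). The SAE incidence can hide about 2 to 10 points at a 10% non-SSI SAE rate, depending on the share of SSIs that are serious. More overlap or a smaller SSI effect reduces these figures.

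The documents do not support the wider claim that the safety analysis as a whole conceals harm: individual terms and the listed endpoints remain readable. The gap matters most for SAEs, where only treatment group and relationship are stated. Sample size and the primary analysis are unaffected.

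**What to change.** In the Adverse Events part of Safety Analyses:

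- State that an SSI is recorded as an AE, or as an SAE, when it meets the protocol's definitions.
- Keep the all-AE and all-SAE summaries as planned.
- Add the overall, by-severity and SAE incidences by arm, excluding AE-log events that match a documented SSI. The match must not use SSIs imputed under Efficacy Analyses, Primary Endpoint, where death or a missing end-of-study assessment counts as an SSI; otherwise genuine events could be dropped.
- State that both sets are read together: the all-event set for net harm, the non-SSI set for harm other than SSI.
- Note in the tables that serious SSI sequelae recorded as separate events remain in the non-SSI set.

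The cost is a few more tables and a reconciliation of the AE log with the Visit 2 SSI record. The needed data are already collected.

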© Confidential IrriMax Corporation		Page 28 of 35

Analysis Populations

Intention-to Treat (ITT)

The intention-to-treat population will be defined as all randomized subjects. Subjects will be assigned to a group based on the group they were randomized to.

Per-Protocol Population (PP)

Within the ITT population, subjects will be considered evaluable if they completed the 30 day follow up visit. Subjects who are withdrawn from the study prior to the 30 day follow up will be designated "non-evaluable" and excluded from the PP population.

Safety Analysis Set (SAS)

The safety analysis set will consist of all randomized subjects who underwent an emergency operation. The safety analysis set will be used for all safety analyses. Subjects will be assigned to a group based on the actual procedure received.

Efficacy Analyses

Primary Endpoint

For the primary endpoint, the number and proportion of patients with a SSI observed within 30 days from the date of emergency operation will be summarized by treatment group, along with the difference and 95% confidence interval for the difference (based on the Wald method). If a patient is missing their end of study assessment, or if they died prior to the end of study assessment, they will be classified as having met the primary endpoint of a SSI. A comparison between treatment groups will be made using the Cochran-Mantel-Haenszal test, stratified by site. The two-sided p-value, the adjusted relative risk (IrriSept/Control) and 95% confidence interval of the relative risk (based on the Wald method) will be reported. The study will be deemed successful if the two-sided p-value for the end of study treatment difference is < 5%.

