Concomitant medications are medications that are taken at any time after enrollment. Concomitant medications will be coded using the WHO Drug Dictionary and summarized by drug class and preferred term for each treatment group. The summaries will present the number and percentage of patients using each medication in each treatment group. Patients may have more than one medication per preferred term. At each level of summarization, a patient is counted once if he/she reported one or more medications at that level.

Disposition

A clear accounting of disposition including, the number and percentage of patients screened, randomized, and completed, as well as the primary reasons for screen failure and reasons for early discontinuation of therapy will be reported overall and by treatment group.

Subjects who withdraw from the study (either voluntarily or involuntarily) or do not complete the required End of Study visit will be designated as "non-evaluable." Any data collected on these subjects will not be used in the final efficacy analysis. For those who withdraw consent, screen fail information will be collected. For those subjects lost to follow-up will be noted in the database as early termination. Subjects who are classified as "non-evaluable" will be replaced to the extent required to enroll 600 evaluable subjects.

Study Number IRR-CT-901-2013-01	Version: 1.0	01AUG2014
© Confidential IrriMax Corporation		Page 31 of 35

Interim Analyses

An interim analysis is planned when approximately 33% and 66% of the total number of patients has been enrolled. The purpose of these interim analyses is to monitor safety and study conduct. At the second interim analysis, the sample size will be re-estimated using the conditional power approach.

All persons involved in the conduct and analysis of the study will remain blinded to the results of the interim analysis.

Test Material Compliance and Accountability:

An initial supply of Study Product will be supplied to the study site, by IrriMax Corporation, at least one (1) week prior to study commencement.

Procedures and instructions for Study Product dispensing and accountability will be provided in the Investigator Site Binder.

Investigator Site Responsibilities:

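### The plan resizes the trial by conditional power, yet justifies no multiplicity adjustment by saying no unblinded interim will use the primary endpoint to change the trial

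*Combined protocol and SAP*

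**What the plan says.** The relevant text is all under Statistical Methodology in the combined protocol and SAP.

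- **Interim Analyses, timing:** "An interim analysis is planned when approximately 33% and 66% of the total number of patients has been enrolled".
- **Interim Analyses, purpose:** "The purpose of these interim analyses is to monitor safety and study conduct".
- **Interim Analyses, re-estimation:** "At the second interim analysis, the sample size will be re-estimated using the conditional power approach".
- **Interim Analyses, blinding:** "All persons involved in the conduct and analysis of the study will remain blinded to the results of the interim analysis".
- **Multiplicity:** besides there being one primary endpoint, the ground given is "no formal unblinded interim analyses that will utilize the primary endpoint to modify the trial, no adjustment for multiplicity is planned".
- **Efficacy Analyses, Primary Endpoint:** "A comparison between treatment groups will be made using the Cochran-Mantel-Haenszal test, stratified by site". Success is a two-sided p-value below 5%. The section also asks for Wald intervals: "the adjusted relative risk (IrriSept/Control) and 95% confidence interval of the relative risk (based on the Wald method) will be reported", and, for the proportions, "along with the difference and 95% confidence interval for the difference (based on the Wald method".
- **Power and Sample Size:** the 600 patients (300 per group) are derived from the primary infection endpoint.

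**The concern.** The reason for testing at an unadjusted 5% is a statement about the interims, and the interim section contradicts it. Resizing the trial according to the interim treatment difference is an unblinded use of the primary endpoint that modifies the trial. It also falls outside the purpose the same section gives for the interims.

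This touches the trial's only confirmatory test. If the sample size follows the interim difference and the final test is the ordinary one, the true level may be above or below 5%, depending on the rule. A reader of this text cannot tell which. The trial is open-label, so it also matters to settle in advance who may see results by arm.

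**Working it through.** **1. The plan's own figure.** Table 2.1 uses n = 300 per group and a two-sided 5% chi-square test. Power = Φ{[(p1 − p2)√n − 1.96√(2p̄(1 − p̄))] / √(p1(1 − p1) + p2(1 − p2))}. For 20% vs 10%: (1.732 − 0.990)/0.500 = 1.485, giving 93.1% against the stated 93%. For 20% vs 14% (the 30% reduction): 49.9% against 50%. The other seven cells also reproduce.

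**2. What conditional power uses.** Let n1 be the patients per arm at the interim, N the final number per arm, n2 = N − n1, and z1 the interim between-arm statistic. Then CP = Φ{[√n1·z1 + n2·θ − 1.96√N]/√n2}. Under the observed trend θ = z1/√n1; under a planned effect θ is fixed. In both cases z1 stays in the formula, so the new N is a function of infection by arm. A re-estimation from the pooled rate would not use z1, but it is not a conditional power method.

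**3. Effect on the level.** Under the null, the type I error is the integral over z1 of φ(z1) times the chance that the final |Z| exceeds 1.96 with N = N(z1). From the plan: 300 per arm, interim at 66%, so n1 = 0.66 × 300 = 198. Assumed, because the text gives no rule: all 198 have outcomes, 90% target under the observed trend, N only increases, and N goes to the cap if the target cannot be reached.

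| Rule | Cap 1.5x | Cap 2x | Cap 3x |
|---|---|---|---|
| No minimum CP, sized for IrriSept benefit only | 5.33% | 5.52% | 5.75% |
| No minimum CP, trend in either direction | 5.66% | 6.05% | 6.50% |
| Increase only if CP ≥ 30%, either direction | 4.65% | 4.52% | 4.45% |
| Increase only if CP ≥ 50%, either direction | 4.65% | 4.56% | 4.55% |

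For benefit-only sizing, the 30% minimum gives 4.72% to 4.82%.

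In the first two rows, false claims in IrriSept's favour rise from 2.50% to 2.83/3.02/3.25%. If a benefit-only rule leaves N at 300 under an adverse trend, they are 2.78/2.89/2.98%. An 80% target with no minimum and either direction reaches 6.83% at 3x.

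**4. If the interim does not wait for 30-day outcomes.** With enrolment over m = 6 or 9 months, n1 = (0.66 × 600 − 600/m)/2 = 148 or 165. With no minimum, the three caps give 5.28–5.30/5.45–5.47/5.64–5.68% (benefit only) and 5.56–5.59/5.89–5.94/6.27–6.35% (either direction).

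**5. A test that holds the level.** Z = √0.66·Z1 + √0.34·Z2, with the weights fixed in advance, has level 5.0% under any rule for N. In a site-stratified simulation (assumed 13 equal sites, control rates 12–28%, benefit only, 90% target, 400,000 null runs), the ordinary CMH test gave 5.34/5.55/5.76% and the weighted one 5.01/5.01/5.03%. With N raised c-fold, the weighted test keeps (0.66 + √(0.34(c − 0.66)))²/c of the effective sample size: 95.1%, 89.1% and 80.3% at 1.5x, 2x and 3x.

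**The case against.** The strongest defence is that a blinded re-estimation was meant and conditional power was loosely worded. The blinding sentence, the purpose sentence and the Multiplicity section all point that way, and this reading is plausible. It still requires a change, because the words as they stand name a method that needs the treatment difference. Blinding the study team limits who sees the result; it does not make the new N independent of it.

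A second defence is that the separate SAP promised under Statistical Methods may set the rule, cap and test. That is fair, and the absence of those details here is not the complaint. But no SAP rule would make the Multiplicity statement true while the re-estimation sentence stands.

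A third defence is that the premise may be false while the conclusion, no adjustment, is still acceptable. This stands: several rules keep the ordinary test below 5%.

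Two stronger readings are tempting. A reader might infer that the 5% level is exceeded; the documents do not support that, because they state no rule. A reader might also infer that the blinding sentence leaves nobody to do the calculation. The Randomization section already uses a statistician from outside the study to prepare the schedule, so such a role exists. The text simply does not assign the interim to that person or anyone else.

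**Conclusion.** The text is wrong as written: the Multiplicity section denies a step that the Interim Analyses section plans. The conclusion rests on the wording and on the definition of conditional power, not on any assumed rule.

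The effect on the level is undetermined. The range of about 4.5% to 6.5% rests on the assumed 90% target under the observed trend, increases only, caps of 1.5 to 3 times, and a normal approximation. Any inflation would be modest, and some rules produce none. The sponsor should correct this before the second interim, but it is not evidence that the confirmatory test is invalid.

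**What to change.** Make the Primary Endpoint, Multiplicity and Interim Analyses sections agree before the second interim, in one of three ways. Under the plan's own Statistical Methods section, a change to the primary analysis method after the study starts needs a protocol amendment.

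1. **Delete the re-estimation sentence.** This is the smallest change. The multiplicity, purpose and blinding statements then agree and the primary analysis is untouched. The cost is losing the chance to resize.

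2. **Replace it with blinded re-estimation from the pooled infection rate**, and add re-estimation to the stated purpose. The Multiplicity section then stands. The cost is that N cannot react to a smaller effect. At 20% vs 14% the pooled rate is 17%; with the planned 50% reduction this implies 22.7% vs 11.3%, which needs only about 229 per arm for 90% power. N stays at 300 and power stays about 50%.

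3. **Keep conditional power.** Correct the multiplicity and purpose statements, name an independent statistician outside study conduct, state a cap and allow increases only. Then hold the level by either route:
   - *A two-stage site-stratified CMH test with fixed weights.* Use 66/34 if the interim waits for 30-day outcomes; otherwise use the planned share with outcomes and count the remaining patients in stage 2. Report intervals that match the test, for example log RR = Σ(w_k·logRR_k/SE_k)/Σ(w_k/SE_k) with SE = 1/Σ(w_k/SE_k), and treat the difference likewise. This costs programming and the efficiency loss shown above. At 20% vs 14% with a 1.5x cap, power is about 63% with a mean of 402 per arm, against about 67% for the ordinary test with no minimum.
   - *The ordinary CMH test, with increases only when conditional power under the observed trend at the planned N passes a stated threshold.* A 50% threshold holds the level for any upward N. Lower ones such as 30% held it for the 90%-target rule but should be verified for the rule chosen. A 50% threshold computed under the planned 20% vs 10% effect does not hold it (5.1% to 5.2% for the same rule). At 20% vs 14% with a 1.5x cap, power is about 53% with the 50% threshold (mean 327 per arm) and 55% with 30%.
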